6.4.10. Multiple Assessments

Sputum samples will be captured daily starting two days before each visit. Thus, each visit will have up to three sputum samples. For the determination of culture conversion, should any sputum samples at that visit be MAC culture positive, that visit is considered positive for MAC. When determining if a subject had 3-consecutive monthly negative sputum cultures, only schedule monthly samples will be used. However, subjects with a positive unscheduled sputum sample culture among the 3-consecutive monthly negative sputum cultures will not be deemed as achieving culture conversion.

For the determination of sustained culture conversion, if a subject has any positive solid media culture whether scheduled or unscheduled after conversion or with at least 3 consecutive positive scheduled monthly liquid media cultures, that subject will not have achieved sustained culture conversion.

6.5. Handling of Missing Data

6.5.1. Missing Efficacy Endpoints

6.5.1.1. Conversion

A sputum culture will be considered missing at the visit only if there are no sputum samples at that visit to culture. Visits with missing sputum cultures prior to subject converting will be considered as positive cultures. This results in the most conservative outcome, ie, most conversion failures.

6.5.2. Missing Start and Stop Dates for Prior and Concomitant Medication

Medications with partial start and stop dates may be considered as a prior, concomitant, or both. If time is needed for analysis purpose, all missing or partial times will be replaced by 00:00 (HH:MM) for start times and 23:59 for stop times using 24-hour clock.

The following algorithm will be applied to missing and incomplete start and stop dates, stop dates should be imputed before start dates:

Concomitant Medication Stop Dates:

- If the stop date is completely missing, the stop date year is missing, or the medication is ongoing, then set the stop date to the last available subject visit date.
- If the day portion of the stop date is missing, then set the day to the last day of the month, if available otherwise set the day to the 31st.
- If the month portion of the stop date is missing, then set the month to December ('DEC').

Concomitant Medication Start Dates:

- If the imputed stop date is after the first dose of study drug (ALIS), then impute the missing portion of the start date as follows:
 - If only the day portion of the start date is missing, then the day will be set to the first ('01') of the month.
 - If both the day and month portions of the start date are missing, then the day and month will be set to the first ('01') of the month and the month will be set to January ('JAN').
 - If the start date is completely missing, then the start date will be imputed first day of the same year (ie, 01Jan) as the stop date.
- If the imputed stop date is on or before the first dose of study drug (ALIS) or completely missing (ie, ongoing), then impute the missing portion of the start date as follows:
 - If the day portion of the stop date is missing, then set the day to the first ('01').
 - If the month portion of the stop date is missing, then set the month to January ('JAN').
 - If the year is missing, then set the year to the screening visit year.

After start dates have been imputed, check that the imputed start date is on or before the imputed stop date. If imputed start date is after the imputed stop date, set the imputed start date to the imputed stop date.

6.5.3. Missing Start and Stop Dates for Adverse Events

For AEs, missing or incomplete onset or end dates will be imputed such that the AE is assumed to have occurred during the study treatment phase (i.e., considered a TEAE) unless the partial onset date or end date, indicates differently. If time is needed for analysis purpose, all missing or partial times will be replaced by 00:00 (HH:MM) for start times and 23:59 for stop times using 24-hour clock.

The following algorithm will be applied to missing and incomplete onset and end dates, end dates should be imputed before onset dates:

Adverse Event End Dates

- If the end date is completely missing or the year portion of end date is missing (even if day or month are present), or the AE is ongoing, then set the end date to the last available subject visit date.

- If the month portion of the end date is missing and the year is present, then set the month to December.
- If only the day portion of the end date is missing, then set the day to the last day of the month.

Adverse Event Onset Dates:

- If the imputed end date is on or after the first dose of study drug (ALIS), then impute the missing portion of the onset date as follows:
 - If only the day portion of the onset date is missing, and the month and year are the same as the month and year of the first dose of ALIS; otherwise the missing day will be set to the first ('01') of the month.
 - If month portion of the onset date is missing and the year is present, and the year is the same year as the first dose of ALIS; otherwise set the month to January ('JAN').
 - If the onset date is completely missing or the year portion of onset date is missing, the onset date will be imputed to the date of first dose of ALIS.
- If the imputed end date is before the first dose of study drug (ALIS), then impute the missing portion of the onset date as follows:
 - If only the day portion of the end date is missing, then set the day to the first ('01').
 - If the month portion of the onset date is missing and the year is present, then set the month to January ('JAN').
 - If the onset date is completely missing or the year portion of onset date is missing, then set the year to the end date year.
- After onset dates have been imputed, check that the imputed onset date is on or before the imputed end date. If imputed onset date is after the imputed end date, set the imputed onset date to the imputed end date.

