6.4.5. Duration

Duration is the time between two dates and may be expressed in days, months, or years. The formulae for deriving duration are:

- Duration (days) = end – start dates + 1
- Duration (months) = (duration [days])/30.4
- Duration (years) = (duration [days])/365.25

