9.2.2. Summaries of Duration of Adverse Events

The duration of serious AEs, serious AEs resulting in hospitalization, and AEs in the ‘respiratory, thoracic and mediastinal disorders’ body system will be summarized.

The duration of AEs will be summarized (n, mean, standard deviation, median, minimum, and maximum) for each system/organ class and preferred term within the system organ class. The total duration is the sum of the duration for all AEs within a subject at the SOC level, for the SOC summaries and within the preferred term for preferred term summary. The maximum duration is the maximum of the durations for all AEs within a subject at the SOC level, for the SOC summaries, and within preferred term for the preferred term summary. The mean duration is the mean of the durations for all AEs within a subject at the SOC level, for the SOC summaries, and within preferred term for the preferred term summary.

The summary table of AE durations will also include a tabulation of the number of events per subject reported in the summary level (ie, SOC, preferred term level).

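### Final SAP 6.5.3 does not limit imputed adverse event end dates to death or last documented contact, so some partly dated events can outlast follow-up and inflate the duration summaries in 9.2.2

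*SAP*

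**What the plan says.** Final SAP 6.5.3 has three end-date rules for adverse events.

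- Date wholly missing, year missing, or event continuing: "or the AE is ongoing, then set the end date to the last available subject visit date".
- Month missing, year known: "If the month portion of the end date is missing and the year is present, then set the month to December".
- Day missing: "If only the day portion of the end date is missing, then set the day to the last day of the month".

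Only the first rule is tied to the subject's follow-up. One consistency check closes the section: "If imputed onset date is after the imputed end date, set the imputed onset date to the imputed end date". It compares onset with end. It does not compare the end with death, last contact or any visit.

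The imputed dates enter the formula in 6.4.5, "Duration (days) = end – start dates + 1", and through it section 9.2.2: "The duration of serious AEs, serious AEs resulting in hospitalization, and AEs in the ‘respiratory, thoracic and mediastinal disorders’ body system will be summarized". That section reports total, maximum and mean duration per subject, by system organ class and preferred term. The list of displays in 11.1 has eight duration tables.

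Final SAP 6.5.2 uses the same uncapped December and month-end approach for medication stop dates. Appendix A (15.1) of the earlier SAP for the accelerated submission closes year-only events on the last day of the year, also without a cap.

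**The concern.** The rules can give a longer duration to the better-documented event. If nothing is known about the end, the event stops at the last visit. If the site knows that it ended in a given year, it can run on to December, past the last time anyone saw or contacted the subject. For a subject who died, the imputed end can fall after death, which is impossible.

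Safety is the primary objective, and the duration tables cover serious, hospitalised and respiratory events. About 200 subjects were expected (Protocol 3.6.1). Once they are split by INS-212 arm and preferred term, many cells will hold few events, and a single overlong duration then sets the maximum and pulls the mean.

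**Working it through.** The plan gives no figure to reproduce. The check applies its own rules to assumed dates.

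**Inputs**
- Duration = end − start + 1 (final SAP 6.4.5).
- Follow-up of up to 13 months (Protocol 3.6.2). At 30.4 days per month (final SAP 6.4.5), 13 × 30.4 ≈ 395 days.
- Imputed day when month and day are both missing: taken as 31 December. Section 6.5.3 does not state it, because its last-day rule covers only a missing day. The parallel rule in 6.5.2 uses the 31st when the month is unavailable. Reading it as 1 December shortens every imputed duration by 30 days.

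**Excess for one event.** Onset cancels, so the excess over a duration capped at last contact is 31 December minus the last-contact date, provided the recorded end year is the year of last contact.

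| Last contact | Excess (days) |
|---|---|
| 15 January | 350 |
| 15 March | 291 |
| 30 June | 184 |
| 30 September | 92 |
| 15 December | 16 |

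The range is 0 to 364 days. If the end year is earlier than the year of last contact, December of that year lies inside follow-up and the excess is zero. If only the day is missing, the excess is 0 to 30 days, and it arises only when the end month is the month of last contact.

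**Inconsistency with ongoing events.** Take onset 2 March and last visit and last contact both 30 June of the same year.
- Ongoing, closed on 30 June: 30 + 30 + 31 + 30 = 121 days.
- Known to have ended that year, month unknown, closed on 31 December: 121 + 184 = 305 days.

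Put that event in a cell with four others of 10 days each:
- Capped: mean (40 + 121)/5 = 32.2 days, maximum 121.
- Uncapped: mean (40 + 305)/5 = 69.0 days, maximum 305.
- The median is 10 days either way.

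**How often a year-only date overshoots.** Assume the last contact falls on day D of a 365-day year, uniformly, and true end dates are uniform over the 395 days before it. The end year equals the contact year with probability D/395, and the overshoot is then 365 − D.
- Share that overshoots: 182.5/395 = 46%.
- Mean excess over all year-only events: (365²/6)/395 = 56 days.
- Mean excess among those that overshoot: 56.2/0.462 ≈ 122 days.

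For a subject followed for only 180 days, the same assumptions give:
- Share: 1 − 90/365 = 75%.
- Mean excess over all year-only events: [365 × 180²/2 − 180³/3 + 180 × 185²/2]/(180 × 365) = 107 days.
- Mean excess among those that overshoot: 107.3/0.753 ≈ 142 days.

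**Effect on a large summary.** The share of year-only events is not given. If the capped mean is 14 days and the share is 1% to 10% (both assumed), the mean becomes 14 + 0.01 × 56.2 = 14.6 to 14 + 0.10 × 56.2 = 19.6 days. Large cells move little; small cells can move a lot.

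**The case against.** Five points can be made for leaving the rule alone.

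1. *An end after the last visit can be true.* Protocol 8.5 has serious events followed beyond the end-of-study visit, and Protocol 5.11 has events that cause withdrawal followed until resolved or stable. This stands. A reader might infer that every imputed end after the last visit is impossible; the documents do not support that. Only an end after death is impossible, and only an end after the last documented contact is unobserved. The cap must therefore not be the last scheduled visit.

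2. *The overshoot is conditional.* A reader might take 182 days, the plain average of 31 December minus a uniformly spread last-contact date, as the typical error. That figure presumes that every year-only event ended in the year of last contact. Follow-up of up to 13 months usually spans two calendar years, so many year-only dates stay inside follow-up. An onset and last contact in the same month also make a poor illustration, because a resolution seen by then would have a known month.

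3. *Most resolved events are untouched.* It would be wrong to conclude that resolved events in general get longer durations than ongoing ones. The problem is confined to partial dates whose imputed end passes the last contact.

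4. *Such dates should be rare.* Adverse events are assessed monthly (Protocol Table 3-1), serious events are reported within 24 hours (8.4.2), and documentation of serious events is fully verified (12.9). This is plausible, but it limits the frequency and does not make the rule right.

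5. *A late end date is the cautious choice.* Section 6.5.3 aims to class uncertain events as treatment-emergent. A cap leaves that intact: in subjects who took at least one dose, neither last contact nor death can precede first dose, so a capped end stays in the same onset-imputation branch. The capped duration is still the longest that follow-up allows.

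**Conclusion.** The point holds as a minor defect. The December and month-end rules have no upper limit, and nothing else in 6.5.3 supplies one. A partly dated resolved event can therefore be dated past death or last contact and be recorded as longer than an ongoing one.

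The sizes above are measured against last contact, not against the unknown true end. The 46% and 122 days depend on the uniform-date assumptions and on reading the day as 31 December.

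The harm is limited to descriptive duration statistics. A reader might infer that counts of treatment-emergent events are inflated too. They are not: under Protocol 9.6 treatment-emergent status depends on when the event starts, and the primary endpoint is a frequency.

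**What to change.** Add to the end-date rules in final SAP 6.5.3: *An imputed end date is the earliest of the imputed date, the date of death, and the last documented contact for that subject (including AE/SAE follow-up contacts after EOS).* The cap should apply to every adverse event, serious or not, because non-serious events that led to withdrawal are also followed beyond treatment.

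In the same edit, state that the day is 31 when both day and month are missing, and add the same cap to the stop-date rule in 6.5.2.

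The cost is a sentence in each section, a line of code for each, and one derived variable for the last-contact date. If the plan is already final, section 2 of the SAP has deviations noted in the clinical study report, and this change can be recorded there.

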7. STUDY POPULATION

7.1. Subjects Disposition

All disposition tables will present the data by INS-212 randomized treatment and total groups as columns in the table. All percentages on disposition tables will use the Safety population as the denominator.

7.1.1. End of Study Disposition

End of Study Disposition - Overall

The end of study disposition overall table will present the number of subjects that were enrolled (ie, screened), safety population, completed study, discontinued from study, and reasons for discontinuation from study. Percentages will only be presented for completed and discontinued study, and reasons for discontinuation.

End of Study Disposition – by Visit

The end of study disposition table by visit will present the number of subjects who discontinued at that visit and the reasons for discontinuation.

7.1.2. End of Treatment Disposition

End of treatment disposition will present the number and percentage of subjects who completed and discontinued treatment for any reason, and the reasons for treatment discontinuation (death, adverse event, protocol deviation, noncompliance with study drug, lack of efficacy, withdrawal by subject, lost to follow-up, physician decision, site terminated by sponsor, study terminated by sponsor, rescue medication, and other). Except for completed, these reasons will appear on both overall and by visit end of treatment disposition tables. The reasons for discontinuation should be presented in descending order of the total column subject count.

End of Treatment Disposition - Overall

The end of treatment disposition overall table will present the number of subjects that completed treatment, discontinued treatment, and reasons for treatment discontinuation.

End of treatment Disposition – by Visit

The end of treatment disposition table by visit will present the number of subjects who discontinued at that visit and the reasons for discontinuation. Percentages on this table will use the Safety population as the denominator.

7.2. Screen Failures

Not applicable.

7.3. Protocol Deviations

The protocol deviation tables will present the Safety population. The number and percentage of subjects will be presented.

7.4. Demographic and Baseline Characteristics

Demographics and baseline characteristics will be tabulated or summarized as appropriate with treatment arm (based on study INS-212) and total columns for the safety population.

Demographic parameters are age, race, ethnicity, sex, and childbearing potential (females only).

Baseline characteristics are contraception (childbearing females only), St. George's Respiratory Questionnaire (SGRQ) total score, SGRQ symptoms score, SGRQ activity score, SGRQ impacts score, SGRQ question 'how do you describe your current health?', SGRQ question 'what best describes your respiratory problems affect you?', EQ-5D-3L visual analog score (VAS), EQ-5D-3L mobility score, EQ-5D-3L self-care score, EQ-5D-3L usual activities score, EQ-5D-3L pain/discomfort score, EQ-5D-3L anxiety/depression score, CRP (biomarker), IL-6 (biomarker), 6-minute walk test (6MWT) distance, 6MWT supplemental oxygen use, 6MWT early termination, 6MWT remaining time (for early termination subjects only), 6MWT distribution of the number of rests, 6MWT vital signs (pre-test, post-test, and change-from-pre-test in heart rate, respiratory rate, systolic and diastolic blood pressures, and oxygen saturation), 6MWT dyspnea score (pre-test, post-test, and change-from-pre-test), 6MWT distribution of dyspnea scores (pre-test and post-test), 6MWT fatigue score (pre-test, post-test, and change-from-pre-test), 6MWT distribution of fatigue scores (pre-test and post-test), audiology tests (decibels at 250, 500, 1000, 2000, 4000, and 8000 Hz in each ear), visit vital signs (height, weight, body mass index [BMI], temperature, pulse rate, respiratory rate, systolic and diastolic blood pressures, and oxygen saturation).

Age, SGRQ scores (total, symptoms, activity, impacts), EQ-5D-3L scores (VAS, mobility, self-care, usual activities, pain/discomfort, and anxiety/depression), biomarkers (CRP, IL-6), 6MWT (distance, time remaining, vital signs, dyspnea score, and fatigue score), audiology (for each ear within each frequency), and vital signs will be summarized descriptively (n, mean, standard deviation, median, minimum, and maximum).

Age will also be categorized into groups 18-45, 46-64, 65+, 75+, and 85+. The groups 65+, 75+ and 85+ are not mutually exclusive, thus the 65+ group will contain all subjects in the 75+ and 85+ groups and the 75+ group will include the 85+ group.

Age groups, race, ethnicity, sex, childbearing potential (females only), contraception (childbearing females only), SGRQ question 'how do you describe your current health?', SGRQ question 'what best describes your respiratory problems affect you?', 6MWT (supplemental oxygen use, early termination, number of rests, dyspnea score, and fatigue score), and PFT prior bronchodilator use status will be tabulated presenting the number and percentage of subjects in each category.

Subject reporting multiple races will appear in each race they reported. Thus, the total number of subjects with the race groups may exceed the total number of subjects in that column. A group of 'not recorded' will be included with the race groups to account for subjects who declined reporting their race.

7.5. Medical History and Medical Conditions Present at Entry

Medical history will be tabulated by treatment and total for the safety population. The number and percentage of subjects will be presented for subjects reporting at least one medical history and by body system/organ class and preferred term within body system organ class. Medical history is coded using MedDRA 19.1.

7.6. Prior Medication History and Medications Present at Baseline

Prior and concomitant medications are coded using the Who Drug Sept16 dictionary. Prior medications, prior MDR (indicated on the CRF) for NTM-MAC, and concomitant medications are presented in separate tables. The number and percentage of subjects reporting at least one medication and by anatomical therapeutic class level 4 (ATC4) and preferred term within ATC4 will be presented.

The number and regimen of prior MDR for NTM-MAC at baseline will be tabulated. This table was provided with the initial analyses (14.1.9.1). Multi-drug regimen medications are classified into ethambutol, macrolide, rifamycin, or other as follows:

Table 5: Multi-drug Regimen Classification

Classification	Medications
Ethambutol	Ethambutol, Ethambutol Dihydrochloride, Myrin Plus ¹
Macrolide	Azithromycin, Clarithromycin, Erythromycin, Roxithromycin
Rifamycin	Rifampicin, Rifabutin, Rifamycin, Rifinah, Rifater, Myrin Plus ¹
Other	Any medication flagged as part of MDR that doesn't fit the above classifications.

¹ Myrin Plus is a combination product containing an ethambutol and rifamycin.

8. EFFICACY

8.1. General Considerations

All analyses of efficacy endpoints will be sorted by the patient's treatment in study INS-212 and will use the Safety Population.

8.2. Statement of the Null and Alternate Hypotheses

Not applicable

8.3. Subgroup Analyses

Not applicable.

8.4. Multiple Comparisons and Multiplicity

As described in [section 5.1](#), multiplicity adjustments are not necessary for initial or the confirmatory analyses as there were no formal statistical hypothesis for the primary endpoints of this study for the initial or confirmatory analyses.

8.5. Analysis of the Primary Efficacy Endpoint

8.5.1. Primary Efficacy Analysis

There is no primary efficacy endpoint for Study INS-312; all efficacy endpoints were secondary or exploratory.

8.5.2. Sensitivity Analyses of the Primary Efficacy Results

Not applicable.

8.6. Analysis of the Secondary Efficacy Endpoints

8.6.1. Culture Conversion

Culture conversion through 6 months and 12 months of treatment will be analyzed across all groups and within groups.

8.6.2. Time to Culture Conversion

The traditional failure time analysis of culture conversion will be based solely on the INS-312 Safety population.

Kaplan-Meier estimates of the time-to-conversion curves will be produced with and without stratification by the prior 2 treatment groups (from INS-212). Median time to conversion together with the 25th and 75th percentiles and their associated 95% CIs will be presented by treatment group and overall. Kaplan-Meier curve for time to Culture Conversion will be provided in a figure.

The following lines provide sample SAS code for the Kaplan-Meier estimates.

```
PROC LIFETEST DATA=input_data METHOD=KM;  
    TIME DAYS*CENSOR(1);  
    STRATA TRT / NOTEST;  
RUN;
```

For the survival curve, DAYS is the number of days from baseline to culture conversion; TRT is the treatment and CENSOR is an indicator variable that indicates whether the subject was classified as having converted (CENSOR = 0) or not having converted (CENSOR = 1).

